9.4.1.2 Clinical Management of TILs and TNILs

Along with assessing the overall tumor response (see Section 9.4.1.1, Tumor Response), each individual lesion will be assessed to determine appropriate clinical management. The RECIST 1.1 (Appendix B) response criteria will also be used to evaluate each individual tumor response.

Individual Lesion Complete Response (IL-CR): Complete disappearance of target lesion (whether measurable or not, and no new lesion(s) at the site of the target lesion) confirmation by an assessment 8 weeks after the end of the injections (Visit 6).

Individual Lesion Partial Response (IL-PR): Decrease in tumor burden $\ge 30\%$ relative to baseline confirmed by an assessment 8 weeks after the end of the injections (Visit 6).

Individual Lesion Progressive Disease (IL-PD): Progression is defined as >20% increase of at least 5 mm in the sum of the longest diameters of the target lesions or increase in tumor burden $\ge 20\%$ relative to nadir (minimum recorded tumor burden) or the appearance of one or more new lesions confirmed by an assessment 8 weeks after the end of the injections (Visit 6).

 Individual Lesion Rapid PD (IL-RPD): Is defined as an increase of >50% in tumor burden for lesions >2 cm in diameter or 100% tumor burden increase for lesion ≤2cm between visits.

Individual Lesion Stable Disease (IL-SD): Not meeting criteria for CR or PR, in

absence of PD (Decrease of tumor size <30% to increase in size <20% of less than 5 mm in the sum of the longest diameters of the target lesions).

	Individual Lesion	Individual	Progressive Disease	Stable Disease
	Complete Response	Lesion Partial	(PD)	(SD)
	(IL-CR)	Response (IL-		
	IL-CR to be	PR)		
	determined at the latest by Visit 6 (8	 IL-PR will be followed and assessed at 	 If IL-PD confirmed in two consecutive visits OR at Visit 6 (8 week 	 IL-SD will be followed and assessed up to
	week follow up), and will be followed for 6	assessed at Visit 6 (8 week follow up)	OR at Visit 6 (8 week follow up), TIL will be withdrawn and	assessed up to Visit 6 (8 week follow up)
	months • No additional	 If IL-SD is documented at 	alternative therapeutic intervention given	 Alternative therapeutic
	 injections will be given to TILs who have achieved IL-CR prior to the 4th injection visit If recurrent at any 	Visit 6 or beyond, alternative therapeutic intervention will be offered	 If subject has additional TILs, will continue study participation If subject has only one, subject will be 	intervention will be offered if no IL-CR or IL-PR is observed by Visit 6.
TILs	point after IL-CR has been documented, then alternative therapeutic intervention offered (surgical excision, radiation, intralesional therapy etc.) based on patient preference	• If IL-PR continues, TIL will be closely followed until Visit 8, where alternative therapeutic intervention will then be offered	 withdrawn If IL-RPD occurs, treatment will be deferred that visit and will be reevaluated next visit. o If IL-PD confirmed, lesion withdrawn from study and alternative 	
			therapeutic intervention ○ If subject has more than one TIL, then lesions will continue to be a part of the study	
TNILs	 IL-CR to be determined at the latest by Visit 6 (8 week follow up), and will be followed for 6 	• IL-PR will be followed and assessed up to Visit 6 (8 week follow up)	 IL-PD at Visit 3 will undergo alternative therapeutic intervention 	 IL-SD will be followed and assessed up to Visit 6 (8 week follow up)
	monthsIf recurrent at any	 Alternative therapeutic 		 Alternative therapeutic

Table 7. Management of individual TILs and TNILs

point after IL-CR ha	s intervention will	intervention will
been documented a	It be offered if no	be offered if no
Visit 6, then	IL-CR is	IL-CR is
alternative	observed by	observed by
therapeutic	Visit 6	Visit 6
intervention offered		

9.4.2 High Resolution Ultrasonography of Squamous Cell Cancer:

The subjects will complete ultrasound assessments of their lesions at screening Visit (0), and at Visit 6 (second follow up visit).

METHOD:

Focused high frequency ultrasound of the skin lesion will be performed in department of medical imaging using clinical ultrasound equipment LOGIQ E9 (GE Healthcare, Milwaukee, WI) and S-3000 (Acuson; Siemens Medical Solutions, Mountain View, CA). Linear array transducers with upper frequencies of 8-18 MHz and 6-18 (5-14) MHz respectively utilized to obtain sonograms. Imaging will be performed using either custom made gel standoff pad or copious amount of cold ultrasound gel acting as standoff, especially in body parts where gel pad could potentially cause image degradation due to poor apposition. Scanning will be done gently without compression to avoid distortion of superficial lesions. Two-dimensional B-mode images will be acquired following transverse and longitudinal sweeps from right to left and from top to bottom. The ultrasound probe will be oriented along the longest dimension of the lesion to obtain sagittal and transverse measurements of the cancer. Calculations of lesion depth will be made at the deepest extension of the mass in either plane. Duplex Doppler will be used to evaluate tumor vascularity; spectral wave pattern and Doppler measurements will also be obtained.

The subjects will receive ultrasound assessments of their TILs at screening visit (0), and at visit 6 (first follow up visit).

IMAGE INTERPRETATION:

Normal anatomy: The three layers of skin, epidermis (thickness 0.06-0.6 mm), dermis (thickness 1-4 mm) and hypodermis (subcutaneous tissues; thickness 5-20 mm) can be visualized on high frequency ultrasound. The epidermis appears as the most superficial, well defined, hyperechoic, linear band producing the "entry echo" between the ultrasound gel and skin, which can be called as epidermal entry echo (EEE). Dermal layer below the epidermis is also hyperechoic, usually less echogenic than epidermis with hair follicles, vessels, and sebaceous glands appearing as hypoechoic areas within it. The hypodermis or subcutaneous tissue layer is hypoechoic with intervening hyperechoic connective tissue septa separating fat lobules. Underneath the skin, superficial fascia covering muscle may be identified linear hyperechoic structure (1, 2). Squamous cell carcinoma (SCC) is the second most common cancer of the skin after basal cell cancer which has a major tendency for local relapse and regional nodal involvement. Tumor infiltrates into the surrounding soft tissues, cartilage and bone. Sonographic appearance of SCC reveals inhomogeneous hypoechoic lesion with

marginal irregularities; Doppler may show the presence of low-resistance pulsatile flow signals within or at the periphery of the tumor. However, it could be challenging to image the cancer in presence of hyperkeratotic epidermis which leads to reflection and attenuation of the ultrasound waves.

Following treatment anticipatory Sonographic changes in the lesion are expected with loss of inhomogeneous hypoechogenecity and reduced Doppler flow. The cancer may become progressively isoechoic with loss of conspicuity.

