9.4 Study Assessments

9.4.1 Tumor Measurements:

Tumor measurements will be done at each visit. Imaging assessment with high frequency ultrasound will be done at baseline and at the second follow-up visit (Visit 6). At baseline, up to 5 TILs that are at least 10cm apart will be selected to be followed over the course of the study. Up to 10 TNILs can be followed with no more than 2 TNILs selected in the same anatomical area as a TIL. Responses in TILs and TNILs will be measured serially. Clinical measurements will be performed with a millimeter measuring tape (Appendix A). All measurements will be selected that will be able to be followed clinically and for ultrasound evaluations. The RECIST 1.1 (Appendix B) response criteria will be used to evaluate tumor response. Individual tumor measurements will also be conducted to determine clinical management of TILs and TNILs. The timeframe for the clinical (primary endpoint) and evaluation will be at Visit 6 and for high-frequency ultrasound (secondary endpoints) at Visit 6 as well.

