9.4.1.1 Tumor Response

Complete Response (CR): Complete disappearance of all TILs (whether measurable or not, and no new lesions at the site of injection) confirmed by an assessment 8 weeks after the end of the injections (Visit 6).

Partial Response (PR): Decrease in tumor burden $\ge 30\%$ relative to baseline confirmed by an assessment 8 weeks after the end of the injections (Visit 6).

Duration of Overall Response (DOR): DOR is when the time measurement criteria are met for CR or PR (whichever status is recorded first) until the first date that recurrence or progressive disease (PD) is objectively documented, taking as reference for PD the smallest measurements recorded since the treatment started. If no recurrence or PD is documented after PR or CR is observed the time measurement will be performed at Visit 6 for PR and Visit 8 for CR.

Durable Response Rate (DRR): Measured from the time measurement criteria are met for CR or PR (whichever status is recorded first) with the response lasting continuously for > than or equal to 6 months. For PD, the reference will be the
smallest measurements recorded since the treatment started.

Time to progression (TTP): This will be measured from the time treatment is initiated until the first date that recurrence or progressive disease (PD) is objectively documented, taking as reference for PD the smallest measurements recorded since the treatment started.

Progressive Disease (PD): Progression is defined as >20% increase of at least 5 mm in the sum of the longest diameters of the target lesions or increase in tumor burden $\ge 20\%$ relative to nadir (minimum recorded tumor burden) or the appearance of one or more new lesions confirmed by an assessment 8 weeks after the end of the injections (Visit 6).

• **Rapid PD (RPD):** Is defined as an increase of >50% in tumor burden for lesions >2 cm in diameter or 100% tumor burden increase for lesion ≤2cm between visits.

Stable Disease (SD): Not meeting criteria for CR or PR, in absence of PD (Decrease of tumor size <30% to increase in size <20% of less than 5 mm in the sum of the longest diameters of the target lesions).

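### IL-PD and IL-SD are written on the subject's sum of diameters, so read literally one growing TIL can put unchanged TILs of the same subject into IL-PD, against Table 7's lesion-by-lesion management

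*Combined protocol and SAP*

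**What the plan says.** Section 9.4.1 announces lesion-level assessment: "Individual tumor measurements will also be conducted to determine clinical management of TILs and TNILs". Section 9.4.1.2 repeats it: "each individual lesion will be assessed to determine appropriate clinical management".

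The four lesion-level categories do not all follow through. IL-CR is rewritten for a single lesion, with the condition "no new lesion(s) at the site of the target lesion". IL-PD is not: "IL-PD): Progression is defined as >20% increase of at least 5 mm in the sum of the longest diameters of the target" lesions. That is the subject-level criterion of 9.4.1.1, ">20% increase of at least 5 mm in the sum of the longest diameters of the target lesions". IL-SD likewise keeps the sum. IL-PD then adds two alternatives joined by *or*: tumor burden up 20% or more over nadir, or new lesions.

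Table 7 acts on one lesion at a time. A TIL with IL-PD confirmed at two visits in a row, or at Visit 6, is withdrawn and treated otherwise. For the rest of the subject's lesions it says "If subject has additional TILs, will continue study participation", and after rapid progression, "If subject has more than one TIL, then lesions will continue to be a part of the study".

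Section 11.4 stops a subject's treatment when 75% or more of the TILs meet the withdrawal criteria.

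**The concern.** A sum over a subject's target lesions has one value per subject. If that value decides IL-PD, all TILs of a subject enter IL-PD together on that limb, whatever each has done, and no TIL remains for which Table 7's continuation provision could operate. An unchanged TIL would be withdrawn, sent to alternative treatment and counted toward the 75% rule because its neighbour grew.

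The loss for such a TIL is bounded. Injections are given at Visits 1 to 4. The earliest confirmation is at Visits 2 and 3, which forfeits the injections at Visits 3 and 4, that is 2 of 4. At Visit 6 little changes for a stable TIL, because Table 7 then offers alternative treatment to IL-SD lesions as well.

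The fault also runs the other way: a sum dilutes growth in one lesion, so a progressing TIL can stay below the threshold.

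**Working it through.** The plan states no figure on this point, so the check compares the texts and then applies the rule to assumed lesion sizes.

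**Inputs**
- Sum limb: rise of more than 20% and at least 5 mm (9.4.1.2, IL-PD).
- Confirmation: two consecutive visits or Visit 6 (Table 7).
- Stopping share: 75% or more of TILs (11.4).
- Rapid progression between visits: more than 50% for lesions above 2 cm; otherwise "100% tumor burden increase for lesion ≤2cm between visits".
- Up to 5 TILs per subject (2.4, 6.1).
- Lesion sizes: assumed. The documents give only the eligible range, above 0.5 cm and below 5 cm. Tumor burden of a lesion is read as its longest diameter.

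**Texts side by side.** Appendix B, which 9.4.1.2 names as the criteria for each tumor, defines one baseline sum for a subject's TILs and one for the TNILs. It has no single-lesion version. No section replaces the sum with a lesion's own diameter for IL-PD or IL-SD. Because the limbs of IL-PD are alternatives, the sum limb suffices even if the tumor-burden limb is read per lesion.

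**Example 1, unchanged TIL drawn in (all sizes below 2 cm).** Two TILs of 10/10 mm at Visit 1, and 15/10 mm at Visits 2 and 3.
- Sum: 10 + 10 = 20 mm; 15 + 10 = 25 mm. Rise 5/20 = +25%, +5 mm. Limb met at two consecutive visits, for both TILs.
- Own diameter: first TIL 5/10 = +50%, +5 mm, progression; second TIL 0%, stable.
- Share meeting IL-PD: 2/2 = 100% by the sum, 1/2 = 50% by own diameter. The 75% rule is crossed only in the first case.
- Rapid progression does not intervene (+50% against 100%), and the second TIL has no partial response to set against IL-PD.

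**How much growth is needed.** With k equal TILs of diameter d and only one growing by g, the limb requires g/(k × d) > 0.20, so g > 0.2 × k × d, and g ≥ 5 mm. For d = 10 mm:
- k = 2: 0.2 × 2 × 10 = 4 mm, so the 5 mm floor binds (+50% of that lesion).
- k = 3: more than 6 mm (+60%).
- k = 4: more than 8 mm (+80%).
- k = 5: more than 10 mm (+100%).

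The effect is therefore conditional, and it needs more growth as the number of TILs rises.

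**Example 2, progressing TIL missed.**
- 20/20/20 to 26/20/20 mm: that lesion 6/20 = +30%, +6 mm; sum 6/60 = +10%.
- The same below 2 cm, 10/10/10 to 15/10/10 mm: that lesion 5/10 = +50%, +5 mm; sum 5/30 = +16.7%.

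In both, the sum limb is not met although the lesion passes both thresholds on its own diameter. The tumor-burden limb catches it only if burden is read per lesion, which the text does not state.

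**The case against.** The strongest reply is that the intended reading is plain. The terms are headed as individual-lesion categories, Table 7 withdraws a single TIL, and a sum taken over one lesion is simply that lesion's diameter. The literal reading also leaves the provision for additional TILs with almost nothing to do on this limb. This stands as a statement of intent, and investigators may well act on it. It does not correct the criterion, which names the target lesions in the plural and rests on an appendix that gives only per-subject sums.

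Other limits also stand:
- Section 4.1 lists a diameter of at least 2 cm as a high-risk feature, and 11.4 separately stops treatment when such a feature is identified in a TIL. Where lesions reach 2 cm, treatment may stop under either wording. Example 1 avoids this; the first case of Example 2 does not, so the 10 mm case is added.
- A TIL that has shrunk by 30% or more may meet IL-PR as well as IL-PD, and no precedence is given.
- The unrestricted new-lesions limb matters little in practice, since on-study skin examinations cover target lesions only.

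Three stronger readings are tempting and not supported:
- *One growing TIL always pulls in the others.* It does so only if the sum rises enough.
- *It will happen often, because 6.1 admits keratoacanthoma-type lesions that double in size in 4 weeks.* This depends on what size means. If it is diameter, growth over the 3 weeks to Visit 2 is 68% (exponential) to 75% (linear), and the sum of equal TILs rises 34–38% with two and 23–25% with three. If it is area, diameter grows 2^(3/8) − 1 = 29.7%, and the sum rises 14.8% and 9.9%, below the threshold. The rate also describes lesions before treatment.
- *The response endpoints are misdefined.* The primary endpoint is a subject-level response that properly uses the sum (16.1.1), and secondary endpoint 7 counts injected lesions with CR or PR, not IL-PD.

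**Conclusion.** The concern holds as a wrongly stated rule. IL-PD and IL-SD use a per-subject quantity for a per-lesion decision. In a subject with two or more TILs this can place unchanged TILs in IL-PD (Example 1: 100% against 50% of TILs, on either side of the 75% rule) and can fail to flag a progressing one (Example 2). The conclusion about the wording needs no assumption. The examples rest on assumed sizes and on reading tumor burden as longest diameter. Subjects with one TIL are unaffected, as is the primary endpoint. How many subjects would be affected cannot be derived from the documents. Given the evident intent, severity is minor to moderate.

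**What to change.** In 9.4.1.2:
- In IL-PD and IL-SD, replace the sum over target lesions with the longest diameter of that lesion. Judge IL-PD against that lesion's own smallest recorded value, keeping the 20% and 5 mm thresholds.
- State that tumor burden in the individual-lesion definitions means that lesion's own measurement.
- Limit new lesions in IL-PD to the site of that lesion, as IL-CR already does.

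The cost is the rewording of two definitions and one added sentence. No threshold changes and no new measurement is needed, because lesions are already measured at every clinic visit. Table 7 and the 75% rule can then be applied as written.

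One consequence should be stated openly. The tumor-burden limb, 20% or more over nadir, has no millimetre floor. Any lesion that meets the limb of more than 20% and at least 5 mm already meets the burden limb, so the 5 mm minimum has no separate effect: a lesion with a 5 mm nadir would reach IL-PD on 1 mm of growth (1/5 = 20%). The same redundancy exists in the present subject-level wording. Whether to add the floor to that limb is for the sponsor to decide.

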9.4.3 Chart Review: Frequency of Nonmelanoma Skin Cancers (NMSCs)

Participants' charts will be reviewed to assess the number of nonmelanoma skin cancers before and after the intervention. The frequency of NMSCs before the intervention will include the 12 months before Visit 1 and the 24 months before Visit 1 if available. The frequency of NMSCs after the intervention will include the 12 months after the last injection visit (or Visit 4) and then 24 months after the last injection (or Visit 4) if available. This exploratory objective is an effort to quantify the abscopal effect those participants may experience.

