9.0 STUDY PROCEDURES

9.1 Screening- Visit 0

Potential subjects will enter the screening period of the study after a completely executed informed consent has been obtained.

- Review of inclusion/exclusion criteria
- Medical and medication history and dermatological history review
- Skin check by the study provider
- Urine pregnancy test (72 hours before enrollment)
- Screening blood work to include a complete blood count (CBC), comprehensive metabolic panel (CMP) and pregnancy test (hCG) if urine pregnancy test comes back positive or inconclusive
- Identification of the target lesions for the study. One subject can have up to 5 TILs. One to three TILs may be on the same anatomical area but will need to be 10 cm apart. Up to 10 TNILs can be followed with no more than 2 TNILs selected in the same anatomical area as a TIL.
- Photographing and measuring of the target lesions
- Biopsy of any suspected non-target skin cancers (ie BCC). If a non-SCC skin cancer is confirmed the corresponding treatment should be completed prior to initiation of study intervention.
- Partial biopsy of lesions suspicious for cSCC (both TILs and TNILs) that have not already been biopsied. A partial shave or small punch biopsy may be done to sample the tissue.
- Vital signs obtained to include blood pressure, pulse, temperature, height and weight
- Ultrasound of TILs at Radiology Department for baseline evaluation (Appendix B)
- Assign screening number starting with the 2-digit site number followed by SCC

and a 3-digit sequential number, starting with -001 and increasing by one for each subject. If a subject fails the screening visit they may be replaced by an additional subject.

9.2 Enrollment- Visit 1

• See 9.3 for enrollment visit details

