9.3 On IP treatment

Registered subjects will be treated with talimogene laherparepvec based on lesion size, administered at of 10⁶ (1 million) PFU/mL administered intralesionally for the first visit and 10⁸ (100 million) PFU/mL administered intralesionally for subsequent visits (V2-4). A full description of treatment plan and dosing is outlined in sections 2.4 and 7.1.

Visit 1- First injection visit (7 - 28 days +/- 3 days)

- Skin exam only of target lesions
- Review of all blood work and confirmation to continue in the study
- Review of the biopsies of SCC lesions to confirm SCC diagnosis
- Assess adverse events
- Assess con med changes
- Complete inclusion/exclusion criteria
- Assign subject study number starting with SCC-01 and continue to be assigned sequentially
- Vital signs
- Photograph and measure all target lesions (Appendix A)
- Inject TILs
- Provide patient education on any side effects to expect and the treatment of the injected sites
- Schedule the next injection visit in 3 weeks

Visit 2- Second injection visit (21 days +/- 3 days)

- Vital signs
- Review con meds
- Assess for any adverse events
- Skin exam only of target lesions
- Photograph and measure all target lesions (Appendix A)
- Inject TILs
- Provide patient education on any side effects to expect and the treatment of the injected sites
- Schedule the next injection visit in 2 weeks

Visit 3- Third injection visit (14 +/- 3 days)

- Vital signs
- Review con meds

- Assess for any adverse events
- Skin exam only of target lesions
- Photograph and measure all target lesions (Appendix A)
- Inject TILs
- Provide patient education on any side effects to expect and the treatment of the injected sites
- Complete bloodwork (CBC, CMP)
- Schedule the next injection visit in 2 weeks.

Visit 4- Fourth injection visit (14 +/- 3 days)

- Vital signs
- Review con meds
- Assess for any adverse events
- Skin exam only of target lesions
- Photograph and measure all target lesions (Appendix A)
- Inject TILs
- Provide patient education on any side effects to expect and the treatment of the injected sites
- Schedule the first follow up visit in 4 weeks.

Visit 5- First follow up visit (28 +/- 7 days)

- Vital signs
- Review con meds
- Assess for any adverse events
- Skin exam only of target lesions
- Photograph and measure all target lesions (Appendix A)
- Schedule the second follow up visit in 4 weeks

Visit 6- Second follow up visit (28 +/- 7 days)

- Vital signs
- Review con meds

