9.5.1 Follow up

Visit 5- First follow up visit (28 +/- 7 days)

- Vital signs
- Review con meds
- Assess for any Adverse Events
- Skin exam limited to all target lesions
- Photograph and measure target lesions (Appendix A)
- Schedule the next follow up visit in 4 weeks.

Visit 6- Second follow up visit (28 +/- 7 days)

- Vital signs
- Review con meds
- Assess for any Adverse Events
- Skin exam limited to all target lesions
- Photograph and measure target lesions (Appendix A)
- Schedule second ultrasound to be completed on TILs before next follow up visit
- Schedule the next follow up visit in 6 weeks.

Visit 7- Third follow up visit (42 +/- 10 days)

- Vital signs
- Review concurrent meds

- Assess for any Adverse Events
- Skin exam limited to all target lesions
- Photograph and measure target lesions (Appendix A)
- Schedule the next follow up visit in 14 weeks.

Visit 8 - Fourth follow up visit (98 +/- 21 days)

- Vital signs
- Review con meds
- Assess for any adverse events
- Skin exam limited to all target lesions
- If sites are free of disease, participant participation will be complete
- Photograph and measure target lesions (Appendix A)
- Complete subject payment form

Visit 9 – Telephone Follow up (356 +/- 31 days) after Visit 1

• Assess for changes of target lesions

• If active lesion(s) are noted by the participant, they will follow up with a dermatologist and their records will be requested

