16.2.8 Chart Review of Abscopal Effect

Summary statistics (counts, percentage, mean, standard deviation, etc.) will be presented for exploratory endpoint as appropriate. Statistical comparison of the number of non-melanoma skin cancers in the 12 month and 24 month period prior to the TVEC injections versus the number in the 12 months after the TVEC injections will be performed using the Wilcoxon Rank Sum Test.

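### The 'before' skin-cancer count takes in a protocol-mandated screening search that has no counterpart after treatment, so the exploratory NMSC comparison leans towards an apparent abscopal effect

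*Combined protocol and SAP*

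**What the plan says.** Section 9.4.3 takes the endpoint from medical records: "charts will be reviewed to assess the number of nonmelanoma skin cancers before and after the intervention". On the earlier period it says: "The frequency of NMSCs before the intervention will include the 12 months before Visit 1 and the 24 months before Visit 1 if available". The later period is 12 months from the last injection (Visit 4), then 24 months if available. Section 16.1.3 repeats these windows.

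Section 16.2.8 plans descriptive summaries and a Wilcoxon rank sum test, with the 12-month post-injection count as comparator: "Statistical comparison of the number of non-melanoma skin cancers in the 12 month and 24 month period prior to the TVEC injections versus". No section says which diagnoses count, excludes cancers found at screening, or adjusts for how often the skin was examined.

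Section 9.1 (Visit 0) lists a skin check and biopsy of any suspected non-target skin cancer, with BCC as the example. It adds: "If a non-SCC skin cancer is confirmed the corresponding treatment should be completed prior to initiation of study intervention". The visit schedule in section 2.4 puts Visit 1 one to four weeks after Visit 0.

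For Visits 1 to 8, section 9.3 specifies "Skin exam only of target lesions". Section 9.5.1 repeats the restriction for Visits 5 to 8: "Skin exam limited to all target lesions". Section 9.6 does the same for early termination, and Visit 9 is a telephone call about target lesions. The schedule in section 26 shows physical examination and skin biopsy at Visit 0 only.

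**The concern.** A before/after count of new cancers can be read only if the search for them is comparable in the two periods. Here the study adds one search for non-target cancers to the 'before' period and none to the 'after' period.

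Visit 0 acts in two ways. Cancers it finds are added to the 'before' count. Prevalent cancers it finds are also removed, and routine care can no longer find them in the 'after' window. Both push the comparison towards a fall, which is the direction section 9.4.3 would read as an abscopal effect. The planned test and the descriptive summaries both carry this bias.

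The point concerns non-target cancers found at Visit 0. Whether the target tumours themselves are counted, whether rank sum suits paired counts, and how the window lengths match are separate questions.

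**Working it through.** **Figures in the plan.** The documents state no NMSC rate, effect size or power for this comparison, so there is nothing to reproduce.

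**Timing.**
- Visit 0 is 1 to 4 weeks before Visit 1. It is therefore inside the 12-month and the 24-month 'before' windows for every subject.
- Confirmed non-SCC cancers are to be treated before study intervention, so their diagnoses precede Visit 1.
- Visits 5 to 8 fall at 4, 4+4 = 8, 8+6 = 14 and 14+14 = 28 weeks after Visit 4. All are inside the 12-month 'after' window, and all are limited to target lesions.

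**Size of the over-count.** Let λ be the yearly number of NMSC found by routine care, the same in both periods, and k the extra non-target cancers per subject found at Visit 0. Neither is in the documents. With 12-month windows and no drug effect:

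apparent fall = [(λ + k) − λ] / (λ + k) = k / (λ + k)

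| λ per year | k = 0.25 | k = 0.5 | k = 1 |
|---|---|---|---|
| 1 | 20% | 33% | 50% |
| 2 | 11% | 20% | 33% |
| 3 | 8% | 14% | 25% |

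**Effect on the planned test.** Simulation with 20 subjects, λ = 2, no drug effect, Poisson counts, and a two-sided rank sum test at 0.05, counting only significant falls:

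| Rates between subjects | k = 0.5 | k = 1 |
|---|---|---|
| One common rate | about 16% | about 46% |
| Gamma-distributed (shape 0.5 to 2) | about 5–8% | about 28–34% |

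With a common rate and k = 0 the figure is about 2.5%. The gamma row is lower because spread between subjects costs an unpaired test power. The expected fall in the mean is the same in both rows.

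**Clearing of prevalent cancers.** A second model lets cancers arise at 2 per year and be found at the next full-skin examination. Visit 0 is placed 2.5 weeks before Visit 1, and Visit 4 is 3+2+2 = 7 weeks after Visit 1. Mean 12-month counts with no drug effect, routine care unchanged:

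| Routine examinations | Before, as planned | Before, ended at Visit 0 without screening finds | After | Fall as planned | Fall after the change |
|---|---|---|---|---|---|
| Every 6 months | 2.41 | about 2.0 | 1.79 | about 25% | about 10% |
| Every 12 months | 2.92 | about 2.0 | 1.34 | about 54% | about 33–34% |

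For example, 1 − 1.34/2.92 = 54% and 1 − 1.34/2.0 = 33%. Redefining the window removes the over-count. It leaves an 'after' window that starts from recently cleared skin.

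**The case against.** The strongest reply is that this is a chart review, not a tally of study-examination findings. Routine dermatology diagnoses enter both windows and dilute the one screening visit. That is true. Unchanged routine care adds equally to both sides, however, and so leaves the Visit 0 surplus in place.

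Closer surveillance after treatment could offset it. In the simple model the break-even ratio of detected cancers, after to before, is (λ + k)/λ. At λ = 2 that is 1.125, 1.25 and 1.5 for k = 0.25, 0.5 and 1. In the second model, moving from 12-monthly examinations before to 3-monthly after still gave 2.90 against 1.98. The plan neither requires nor records such a change. A reader might infer that the count must fall by construction; the documents support only an expected fall under unchanged incidence and routine care.

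The assumed yield is also uncertain. Section 9.1 does not say the skin check covers the whole body, although biopsying any suspected non-target cancer implies looking beyond the target sites. Some SCCs found at Visit 0 may be selected as target lesions, which leaves mainly BCCs and unselected SCCs. The range for k therefore has no anchor in the documents.

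Nor should 16% and 46% be read as the error rate of the planned test. They require every subject to share one rate, which is unlikely when section 1.2 admits both single-lesion and multiple-lesion patients.

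Finally, the endpoint is exploratory, in a single-arm trial of about 20 subjects, and the Simon rule uses ORR. This limits the importance of the point but does not make the comparison interpretable.

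**Conclusion.** The point holds as a detection asymmetry with a known expected direction and an unknown size. The 'before' windows include a mandated search for non-target cancers, and no study examination after Visit 0 looks beyond target lesions. With incidence and routine care unchanged, the NMSC count is expected to fall without any drug effect.

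At an assumed 2 NMSC per year and 0.25 to 1 extra cancer per subject, the apparent fall is 11% to 33%. The chance of a nominally significant fall by rank sum, at 0.5 and 1 extra cancer, is about 16% and 46% with one common rate, and about 5–8% and 28–34% when rates vary between subjects. All of these rest on assumed inputs.

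A reader might also infer that redefining the window cures the problem, or that the trial's main result is in doubt. Neither follows: clearing of prevalent cancers leaves a residual bias, and the ORR analysis does not use these counts. This is a cheap improvement.

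**What to change.** In sections 9.4.3, 16.1.3 and 16.2.8:

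1. End the 12-month and 24-month 'before' windows at Visit 0, ahead of the screening skin check.
2. Exclude cancers diagnosed from Visit 0 screening biopsies from both windows.
3. Extract from the same charts the number of full-skin examinations in each window, and report the NMSC counts alongside it.
4. State as a limitation that this reduces but does not remove the bias, because Visit 0 clears prevalent cancers before the 'after' window opens. A fall in NMSC should not be read on its own as evidence of an abscopal effect.

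Settle the definitions before charts are abstracted. The cost is wording in three sections, one extra chart-review field and slightly fewer 'before' cancers. No visit or procedure is added.
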